Secondary measures: outcomes and mediators. We will compare rates of treatment retention and recurrence of substance use to the general rates reported by NUWAY. We will also examine pre-post treatment means and standard deviations of hypothesized mediators (affect, satisfaction with recovery, individual items theoretically related to PPJ) to determine if change is in the expected direction. We will also study these constructs to determine if there is reasonable variability in the data we collect or if floor or ceiling effects are present. We may also use single-subject designs⁵⁶ to depict change over time in key constructs by study participant. Qualitative data will be thematically analyzed using the techniques recommended by Braun and Clarke.¹³ Here, the researcher examines transcripts of texts and identifies key themes and how themes relate to one another. These data will inform intervention development and study implementation procedures.

Data analytic techniques to compare treatment and control groups. While this pilot study will not be adequately powered to detect significant effects between treatment and control groups, we will compare differences between the treatment and control groups at baseline and over time using either t-tests or multi-level modeling. T-tests will reveal significant differences between groups and multi-level modeling will show whether rate of change is significantly different between groups.

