13.1. Withdrawal Circumstances: Participants will be withdrawn from the research without their consent for three reasons: 1) if the participant leaves NUWAY treatment against staff advice, 2) if the participant leaves NUWAY treatment at the request of staff for breaking the rules (for example, if they instigate a physical altercation), or 3) the participant leaves NUWAY treatment without discussion with staff and does not return. In these three situations, we would retain the person's data to date and code them as having discontinued treatment, since treatment retention is one of our primary outcomes. Participants of course can keep any Target gift card credits they have earned. If a participant leaves treatment and the study owes the individual Target gift cards, these will be distributed electronically.

13.2. Withdrawal Procedures: Participants can elect to leave the study at any time. This is emphasized in the informed consent document. If participants leave the study, we will still consult NUWAY records to determine relapse or

treatment departure for all study participants. We will include this information in the informed consent document.

Termination Procedures: If a participant stops participating in study activities, we will reach out to them up to 2 times and ask them if they would like to leave the study. If they say no then the process will stop and we will pay them any Target gift cards we owe them. If they are uncertain, we will warmly invite them to return to study activities, but will then consider them to have left the study if they do not return. We may also ask NUWAY staff to help us find out this information. If a person wishes to leave the study, we will note this in our study records. For individuals who leave the study prematurely, we will use data already collected and follow up data on relapse and treatment departure in our data analyses. Participants of course can keep any Target gift card credits they have earned and we will pay out any additional Target gift cards earned upon their exit from the study.

NUWAY study participants will be required to sign a release of information naming research staff, so that research staff and NUWAY staff can communicate with each other. If study participants call research staff by telephone, we will be able to call them back at NUWAY and speak to them or leave a message.

14. Risks to Participants

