17.2. Power Analysis: Preliminary data from existing behavioral activation (BA) research was used to determine power for the original proposal with N=76. For the outcome of abstinence (yes/no), previous work found outcomes for this variable of 41.5% for the BA group and 24.8% in the control group.¹⁴ For a 1-tailed test with $p < .10$, our power to detect a significant effect for abstinence (yes/no) in the proposed study would be .61 (for a 2-tailed test with $p < .05$, power would be .34). For the outcome of treatment retention (yes/no), previous work showed 96.6% for the BA group and 75.9% in the control group.¹⁶ For a 1-tailed test with $p < .10$, our power to detect a significant effect for treatment retention (yes/no) in the current study would be 94% (for a 2-tailed test with $p < .05$, power would be .82). Therefore, we should be adequately powered to detect statistically significant differences for the outcome of treatment retention in the current study using a 2-tailed test. R was used to conduct these power analyses.⁶¹

17.3. Statistical Analysis: This pilot study will not be adequately powered to detect an effect. Still we will compare the treatment and control groups using t tests and multi-level models to determine differences in means and in slopes between the groups, respectively. Descriptive statistics of the quantitative measures will be used to conduct power analyses and sample size calculations for a larger controlled trial. Also, multi-level analyses will

be conducted to determine significant change over time in factors of interest. We will also be able to examine whether change over time varied by certain subgroups (e.g., those with lower versus higher levels of the factor of interest at baseline).

17.4. Data Integrity: The use of Qualtrics to collect survey data will improve data accuracy because this allows us to avoid keystroke and other errors involved with manual data entry from written questionnaires. We will scrutinize the data produced by Qualtrics to ensure its integrity; whether values are within scale ranges and whether missing data is coded correctly. We will carefully examine and clean the data to ensure accuracy. For standardized instruments, we will be very careful to follow the directions for summing or taking the mean of scale items and reverse code any items as per the instructions.

18. Confidentiality

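### Later mediator means are compared by t-test among responders only, although being a responder depends on retention; take those differences from the multi-level model already planned

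*Combined protocol and SAP*

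**What the plan says.** **Choice of test.** In section 5.2, under Analysis Plan, the arms are to be compared "at baseline and over time using either t-tests or multi-level modeling". The text continues: "T-tests will reveal significant differences between groups and multi-level modeling will show whether rate of change is significantly different between groups". Section 17.3 is more definite: the arms are compared "using t tests and multi-level models to determine differences in means and in slopes between the groups, respectively". So means go to t-tests and slopes to models.

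**Who is withdrawn.** Section 13.1 states: "Participants will be withdrawn from the research without their consent for three reasons: 1) if the participant leaves NUWAY treatment against staff advice". The other two reasons are being asked to leave and leaving unannounced without returning. For these people "we would retain the person's data to date and code them as having discontinued treatment". For early leavers in general, section 13.2 adds only later information on relapse and treatment departure.

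**Who is still contacted.** In section 5.2, the text for both arms says that people who lapse keep receiving surveys and that dropouts are offered a shortened exit interview. Section 5.3 invites people discharged on good terms to the exit interview. Neither place says whether the people withdrawn under 13.1 are covered.

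**Missing data.** Section 17.4 checks that missing values are coded correctly. No analysis set, imputation method or sensitivity analysis is given for the mediators.

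**The concern.** Retention is a primary outcome (section 3.1), and PPJ is hypothesised to raise it (section 5.1). A later t-test on mood, craving or life satisfaction therefore compares groups that have been selected on something the intervention may change. If people who leave tend to be doing worse and more of them leave the control arm, the remaining controls look better than the randomised control arm would have. The difference in means is then pulled against PPJ.

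The t-test also discards what is already in hand. Someone who answered the baseline and Phase 1 surveys and then left contributes nothing to a t-test at the end of Phase 2. The multi-level model can use those surveys, but the plan assigns it to slopes.

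The pilot's small size does not answer this: low power concerns precision, not bias. Section 17.3 also says descriptive statistics from this study will inform the sample size of a larger trial.

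**Working it through.** Scores are taken as coded so that higher is better; for craving or negative affect the signs flip.

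**1. The plan's own figure.** Section 17.2 uses N=76 and, for retention, says "previous work showed 96.6% for the BA group and 75.9% in the control group". It gives power .82 (two-tailed .05). With 38 per arm (equal allocation assumed) and the arcsine effect size:

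- h = 2·asin(√0.966) − 2·asin(√0.759) = 0.655
- power = Φ(0.655 × √(38/2) − 1.96) = Φ(0.895) ≈ 0.815

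This reproduces .82, so these are the plan's working retention rates.

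**2. How many would have a late score.** If everyone not retained is missing:

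| N | PPJ | Control | SE of difference, √(1/n₁ + 1/n₀) |
|---|---|---|---|
| 76 | 38 × 0.966 = 36.7 | 38 × 0.759 = 28.8 | 0.249 SD |
| 100 | 50 × 0.966 = 48.3 | 50 × 0.759 = 38.0 | 0.217 SD |

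**3. Shift from selection.** Suppose leaving happens after the Phase 1 survey and the propensity to stay correlates λ with the Phase 1 score. Let r be the between-visit correlation. The mean of those remaining then rises by λ·r·φ(c)/p, where p is the proportion retained and c = Φ⁻¹(1 − p). The documents give neither λ, r nor the timing; all three are assumptions.

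- φ(c)/p is 0.078 at p = 0.966 and 0.411 at p = 0.759. The gap is about −0.332 before rounding.
- φ(c)/p is 0.195 at p = 0.90 and 0.350 at p = 0.80. The gap is −0.155.

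Bias of the t-test difference = gap × λ × r:

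| Retention | λ=0.2, r=0.5 | λ=0.5, r=0.5 | λ=0.5, r=0.7 | λ=0.8, r=0.7 |
|---|---|---|---|---|
| 96.6% vs 75.9% | −0.033 | −0.083 | −0.116 | −0.186 |
| 90% vs 80% | −0.016 | −0.039 | −0.054 | −0.087 |

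Simulation gives the same ranges within simulation error (−0.03 to −0.18 and −0.01 to −0.09). With equal retention, or with λ = 0, the bias is 0. With negative λ it favours PPJ.

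**4. A second route.** At the plan's rates, (0.966 − 0.759)/0.966 = 21% of PPJ completers would be people retained only because of PPJ. If they score 0.2, 0.5 or 1.0 SD below the others, the completer difference shifts by 0.214 times that: −0.04, −0.11 or −0.21 SD.

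**5. What the model recovers.** These are simulations at 96.6% vs 75.9%.

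- Leaving depends on recorded scores, true effect 0.30 SD, λ 0.5 to 0.8, r 0.5 to 0.7: the t-test averages 0.12 to 0.21 SD. A maximum-likelihood estimate from all surveys averages 0.30 SD, with about the same standard error.
- Leaving depends on the unseen final score (correlation 0.5), true effect 0: completers −0.16 SD, mixed model −0.11 SD. Across the settings tried, the model removed about a quarter to just over half of the bias.

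**The case against.** **Direction is not given by the documents.** A reader might infer that a retention benefit must make PPJ look worse on every mediator. That needs PPJ to raise retention and the extra people retained to score worse on the measure in question. The plan reports no correlation between leaving and any mediator. In the development study, commitment to sobriety was already near the top of its scale, so one direction cannot be presumed for all measures. This stands: the bias is conditional, and it can be zero or reversed.

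**Not every comparison is exposed.** Section 5.2 allows either method, and section 17.3 plans slope models that can use leavers' earlier surveys. Retention and substance use come from the treatment record. This stands: only later t-tests of mediator means are at issue.

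**Leavers may still answer.** A reader might infer that rule-withdrawn people give no further scores. The continued surveys and shortened exit interview in section 5.2 leave that open. If these people do respond, the bias shrinks. The t-test would still ignore earlier scores for anyone who does not.

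**The inputs are soft.** The 96.6% and 75.9% come from a behavioural-activation trial whose listed title concerns residential treatment, while two of the three NUWAY sites are outpatient. Nothing says when people leave; outpatient treatment generally runs 90 to 120 days, and priority goes to clients who will stay for the study. In the development study 73.3% (11 of 15) left on good terms. The range must therefore be read as illustrative, and at 80% to 90% retention it roughly halves.

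**The bias is below one standard error, on secondary outcomes, in a pilot.** True, and it limits the importance. It is no reason to prefer the t-test when the better estimate needs no new data.

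**The model is not a full cure.** Its unbiasedness in the first simulation follows from letting leaving depend on recorded scores. The second simulation shows that part of the bias remains otherwise, which is why a sensitivity analysis belongs in the fix.

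**Conclusion.** The point holds as a cheap improvement. Sections 5.2 and 17.3 give later differences in mediator means to a test that can use only people with a score at that visit. Section 13.1 makes having a score depend on retention, and no missing-data method covers the gap.

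The size rests on assumed leaving-score correlations of 0.2 to 0.8, between-visit correlations of 0.5 to 0.7, and leaving related to the Phase 1 score. On those assumptions the bias is about −0.03 to −0.19 SD at the plan's retention rates and −0.02 to −0.09 SD at 90% vs 80%.

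A reader might go further and infer that the next trial's sample size will be wrong. Section 17.3 says descriptive statistics will be used; it does not name the t-test difference as the planning effect. If it were used, planning on 0.20 instead of 0.30 SD would multiply the sample by (0.30/0.20)² = 2.25, but the plan does not commit to that.

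**What to change.** In sections 5.2 and 17.3:

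1. Estimate the between-arm differences in means at the end of Phase 1, the end of Phase 2 and 1 month from the multi-level model already planned. Use arm-by-visit terms and maximum likelihood, with all randomised participants and all their surveys, including those completed before leaving.
2. Keep t-tests after baseline only as a description labelled complete-case.
3. State that the model assumes missingness depends on observed scores.
4. Add one simple sensitivity analysis, for example shifting leavers' unobserved scores downward by a stated range of SDs and reporting how the difference moves.

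Separately, reconcile section 13.1 with the contact procedures in section 5.2, so that it is clear whether people withdrawn by rule still receive surveys and the shortened exit interview.

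The cost is wording plus one short extra analysis. The model and the surveys are already planned. In the simulations where leaving depended on recorded scores, the model's standard error was about the same as the t-test's.

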Every effort will be made to conduct the exit interviews in person, but when that is not possible, we will offer the opportunity to complete the exit interview via Zoom, telephone or in writing through email. For electronic administration, first choice delivery will be Zoom followed by telephone or writing through email.

Follow-Up Interview. This takes place for treatment and control groups 30 days after the exit interviews. Here, participants answer a few questions about substance use and journaling since we met with them last. Before this interview, participants will be asked to complete their final Qualtrics questionnaire.

Data Capture. Participants in the treatment group will take a snapshot of their journal entries and upload this image to a Qualtrics survey to affirm that assignments are completed; this skill will be taught and practiced during the screening meeting and Group Phase and practiced during the Independent Practice Phase. Participants will learn how to do this using Qualtrics and smartphones or tablets during group and will be able to continue to use their own smartphones or tablets to continue this practice during The Independent Practice Phase. After uploading the image of their journal, participants will answer psychometric questionnaires in Qualtrics. Study iPads will be physically secured when not at use in a staffed office/

supervised storage space (e.g., cabinet or drawer) at NUWAY. Participants will be asked to complete their journal entries right before they upload them to Qualtrics. Individuals in the control group will simply fill out the Qualtrics surveys at the same schedule as the treatment group.

Participants' written entries into their journals is also data of interest to us, including what they write and how many items they write under each category. NUWAY is outpatient versus our previous host site which was residential so we suspect there will be greater incidence of people arriving to group without their journals (having left them at home for example). Participants will have the option to leave their journals on site at NUWAY with staff in a supervised storage space (e.g., cabinet or drawer). Forgetting one's journal is less of a worry during stay-at-home electronic administration.

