Please note we will thank NUWAY staff members by citing NUWAY and perhaps individual staff names in the acknowledgments section of academic presentations, posters, and manuscripts that result from these data. We may make periodic presentations to NUWAY staff about study observations and findings throughout the study period and afterward. When appropriate, we will offer CEUs for Social Workers to NUWAY staff for their attendance at these presentations and host inexpensive lunches or coffee hours for NUWAY staff (who are still working from the office during COVID19 at this time). When we are able, we will present NUWAY staff with honoraria as a gesture of thanks for their help with recruitment.

Data capture will also take place using REDCap. We will use REDCap to keep track of our screening procedures and study participation activities.

Measures. Sociodemographic factors will be assessed at the initial baseline measurement (e.g., age, sex, marital status, years of education, race/ethnicity, employment status, and annual household income). A variety of psychometric scales will be used at baseline and throughout the study. Please see Table 2 for the Schedule of Assessments and the text following after Table 2 for more detail about each assessment approach.

Contents of Qualtrics survey and REDCap survey are described herein in full.

Table 2. Schedule of Assessments.

PROTOCOL TITLE: Journaling and Addiction Recovery

VERSION DATE: 13 April 2021

	How long does it take to complete each of these measures	Baseline	At Every PPJ Qualtrics upload	Asked or Tallied after Group Phase Ends (Phase 1)	Asked or Tallied after Independent Practice Phase Ends (Phase 2)	Final Study Activities including 1 Month Follow-up
Baseline characteristics						
Sociodemographics, including current housing situation, i.e., "are you now living in sober living?"	3 minutes	X				
Hospital Anxiety and Depression Scale	3 minutes	X		X	X	X
10-item SIP-AD, addiction consequences	5 minutes	X				
Commitment to Sobriety (full scale)	2 minutes	X		X	X	X
Trait gratitude	2 minutes	X		X	X	X
AA Affiliation Scale	2 minutes	X				
Exposure to trauma	1 minute	X				
Using Medication Assisted Treatment	½ minute	X				
Legal issues: current involvement in civil legal case and current involvement in criminal court case	½ minute	X				
Satisfaction with treatment	2 minutes			X	X	X
Social Desirability Scale	4 minutes	X				

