Open ended questions: Experience with 10 th step, journaling, gratitude practices, and using a planner.	4 minutes	Verbally administered using REDCap			Verbally administered using REDCap	Verbally administered using REDCap
What have you already heard about the study?	1 minute	Verbally administered using REDCap				
Hypothesized Mediators						
Positive and Negative Affect Schedule, including three items comprising the serenity subscale	2 minutes	X	X	X	X	X
Abstinence Self Efficacy Question (single item)	1 minute	X	X	X	X	X
Commitment to Sobriety (single item)	2 minutes		X	X	X	X
Alcohol craving (single item)	½ minute	X	X	X	X	X
Drug craving (single item)	½ minute	X	X	X	X	X
Happiness with Recovery (single item)	½ minute	X	X	X	X	X

PROTOCOL TITLE: Journaling and Addiction Recovery

VERSION DATE: 13 April 2021

Individual items to assess specific impact of PPJ journaling practice ¹ (attached as "single items to assess change")	3 minutes	X	X	X	X	X
Satisfaction with Life	1 minute	X	X	X	X	X
Quality of life scale, modified to compare quality of life during recovery ("now") to quality of life during active addiction ("then") ¹	3 minutes	X	Global quality of life item only	X	X	X
Flourishing scale	2 minutes	X		X	X	X
Treatment Group Only						
# of Qualtrics surveys completed				X	X	X
Ease, helpfulness, satisfaction, effort of PPJ (for control group, ease, helpfulness, satisfaction, effort of filling out the survey questionnaires)	2 minutes		X	X	X	
# group sessions attended				X		
# homework assignments completed				X		
# journal entries completed				X	X	
Count of # of items entered into PPJ		X	X	X	X	
Eligibility rate and consent rate (treatment and control group)						X
On approximately the fourth session of group (halfway through the total # of sessions) ask: "what is working for me in this journaling group is...." And "what is not working for me in this journaling group is...."						
Open Ended Survey Question						
Treatment group: What are your thoughts about Positive Peer Journaling (PPJ) so far?	2 minutes			X	X	
Outcomes						
Recurrence of Substance Use				X	X	X
Treatment Retention at NUWAY (successfully exiting treatment with staff approval versus against staff advice or at staff request)				X	X	X
Qualitative Exit Interview	45 minutes					X
1 month follow up interview	25 minutes					X

Baseline characteristics.

- Sociodemographics

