Recurrence of substance use and treatment retention will be assessed via NUWAY treatment record. Research staff will not have direct access to the NUWAY treatment record. A NUWAY staff member will meet with research staff at reasonable intervals to report information about treatment retention and recurrence of substance use for study participants from the NUWAY treatment record (for electronic administration, these meetings will be via Zoom or telephone). Recurrence of substance use is assessed at NUWAY by positive urine analyses (UAs) and other drug screens as well as resident self-report. At or after this meeting, research staff will use the password protected electronic document which links participants' real names with their study codenames/numbers. Research staff will use this key to record the information from NUWAY staff into a de-identified database (e.g. excel or SPSS or Google drive) or into REDCap.

[name], the lead investigator, will keep a log/personal notes throughout the study, qualitatively recording observations, especially during recruitment and after each class session.

A de-identified participant tracker will be maintained on Google drive using only participant codenames to track group attendance, independent practice phase activity and other study activities.

Analysis Plan.

Sample characteristics. We will aggregate information about the demographics and baseline characteristics of the study to be able to describe the psychosocial, demographic, and clinical profile of study participants. We will calculate means and standard deviations for continuous measures (e.g., age) and calculate percentages for categorical measures (e.g., marital status).

Primary feasibility and acceptability measures. We will aggregate information designed to assess feasibility and accessibility such as number of Qualtrics surveys completed, group sessions attended, journal entries completed, as well as participant assessment of the difficulty, ease, helpfulness, satisfaction, and effort expended on PPJ. We will sum these items and calculate means and standard deviations.

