If participants leave NUWAY on good terms during the study period, they may still be able to continue to be in the study because it is possible to continue study activities from outside of NUWAY for the independent practice phase. Any smartphone or tablet can be used to continue to participate in the independent practice phase. We may reach out to participants who continue to participant in this way to encourage them to continue in the study or ask if they wish to remain in the study using the contact information they provide to use through NUWAY Inc.

Follow up Interview: At approximately 30 days after the exit interview, we will follow up with participants. Zoom is the first choice but a telephone interview is acceptable for this procedure. We will ask participants about any substance use and journaling in the past 30 days. We will ask a few additional qualitative questions such as what was most memorable about being in the research study, and other similar questions. Participants will be encouraged to complete their final Qualtrics survey before this interview.

- 5.4. Individually Identifiable Health Information: Research study staff will meet with NUWAY staff at reasonable intervals to collect data on our primary outcomes: 1) treatment retention and 2) recurrence of substance use. At these occasions we will go through our list of study participants and ask NUWAY staff if: 1) that person has left treatment or been asked to leave; 2) that person has had a positive urine analysis screening indicating recurrence of substance use. We will mark down the replies in our deidentified data file. If the participant cannot remember date of entry into NUWAY, we will also gain this information from NUWAY staff and the treatment record. To facilitate this work, study staff will use a password-protected file linking participants' real names with study IDs (codenames/numbers).

6. This study therefore includes PHI and therefore we have combined our informed consent document with the appropriate text from a HIPAA authorization form.

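### Recurrence of substance use is defined from the NUWAY record alone, so use between an early good-terms discharge and the follow-up recall window has no stated source or coding rule

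*Combined protocol and SAP*

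**What the plan says.** - **Outcome source.** Section 5.2 (Outcomes): "Recurrence of substance use and treatment retention will be assessed via NUWAY treatment record". The same section gives the record's content: "Recurrence of substance use is assessed at NUWAY by positive urine analyses (UAs) and other drug screens as well as resident self-report". Section 20.2 agrees. Section 5.4 is narrower. Staff there ask NUWAY only whether "that person has had a positive urine analysis screening indicating recurrence of substance use".
- **Timing.** The Table 2 row "Recurrence of Substance Use" is marked after Phase 1, after Phase 2 and at the final activities including the one-month follow-up. It is not limited to one arm.
- **Research question on use.** Sections 5.2 and 5.3 describe one, at the follow-up interview about 30 days after the exit interview. Section 5.3 says "We will ask participants about any substance use and journaling in the past 30 days". Section 5.2 says "participants answer a few questions about substance use and journaling since we met with them last".
- **Surveys and exit interview.** Table 2 and the measures list contain craving items but no item on actual use. The described exit-interview content is the experience of the study and of PPJ, logistics, and journaling, gratitude, 10th-step and planner habits. Section 14.1 nevertheless names substance use among the questionnaire topics.
- **Good-terms leavers.** They are invited to the exit interview, and section 5.3 adds that "they may still be able to continue to be in the study because it is possible to continue study activities from outside of NUWAY". That sentence goes on to limit this to the independent practice phase. Section 13.1 withdraws three other kinds of leaver, not these.

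**The concern.** Drug screens and disclosures to counsellors depend on the client attending NUWAY. Once a client is discharged with approval, an empty record can mean either no use or no observation, and the plan does not separate the two. The follow-up interview could fill part of the interval, but as worded in section 5.3 it starts only at about the exit interview, and section 5.2 does not feed its answers into the outcome.

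The gap is also linked to the other primary outcome. Table 2 treats leaving with staff approval as retention success, which PPJ is expected to increase, and approved leavers are the clients whose record stops. If the arms differ in when clients are discharged, they differ in how long use can be detected. The direction cannot be predicted: earlier approved discharge shortens detection time, and longer stays bring more testing.

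**Working it through.** **The plan's own figures.** The plan states no early-discharge rate and no amount of unobserved time, so there is nothing on this point to reproduce. The nearest figure is the abstinence power in section 17.2. With N=76 (38 per arm, 1:1 assumed) and 41.5% against 24.8%, the pooled two-proportion normal formula gives 0.606 (one-sided 0.10; stated .61) and 0.337 (two-sided 0.05; stated .34). It reproduces. It takes abstinence as known for everyone.

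**Timeline.** Exit is at the five-week mark (section 8.1), day 35. Follow-up is about 30 days later, day 65. A 30-day recall covers days 35 to 65. For a good-terms discharge on study day d, before day 35:

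| Interval | NUWAY record | Research question on use | Counted under 5.2 |
|---|---|---|---|
| Day 0 to d | Yes | None listed | Yes |
| Day d to 35 | Ended | None under the 30-day wording | No source |
| Day 35 to 65 | Ended | Follow-up interview | Not in the rule |

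That the record ends at discharge is an inference: a client who no longer attends gives no samples there. The middle interval lasts 35 - d days: 28 for d=7, 21 for d=14, 14 for d=21 and 7 for d=28.

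**Does the other wording close it?** If the exit interview was held, the last meeting was at about day 35 and the two windows coincide, so days d to 35 stay uncovered. If it was missed, the section 5.2 wording reaches back further, by an amount that depends on what counts as the last meeting. The combined script for those who missed exit is an attachment that the documents do not reproduce.

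**Who is affected.** Section 23.1 gives outpatient stays of generally 90-120 days. A client enrolled on treatment day s reaches exit on day s+35 and follow-up on day s+65.

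- Enrolled on day 14: exit on day 49, follow-up on day 79, both inside a 90-day stay.
- Gap before exit: s above 90-35=55, or above 120-35=85.
- Record ends before follow-up: s above 90-65=25, or above 120-65=55.

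Section 9.1 sets a minimum time in treatment but no maximum. No stay length is given for NUWAY III.

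**Size, under assumptions.** Let 10-30% leave on good terms, on average midway through the five weeks (gap 2.5 weeks), with a weekly risk of use of 3-5%.

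- Risk over the gap: 1-0.97^2.5 = 7.3%; 1-0.95^2.5 = 12.0%.
- Missed recurrence: 0.10 x 7.3% = 0.7 points; 0.30 x 12.0% = 3.6 points.

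With equal early discharge and equal risk, both arms lose the same amount and the difference between them is unchanged. If early discharge were 30% in one arm and 10% in the other, the spurious difference would be (0.30-0.10) x 7.3% = 1.5 to (0.30-0.10) x 12.0% = 2.4 points, against a planning difference of 41.5-24.8 = 16.7 points.

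**The case against.** The strongest reply is that recurrence is measured during the intervention. A reader might infer that the five weeks have no research measure in either arm. That is wrong: the clinic record is a person-by-person source in both arms, scheduled after each phase, and section 13.2 has it consulted even for people who leave the study. Preferring drug screens to recall is a legitimate choice. A reader might also infer that use by good-terms leavers is never observed. That is too broad, since use before discharge is in the record and use in the last 30 days is asked about. Both replies stand and confine the point to the time after discharge.

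Section 14.1 says questionnaires cover substance use, and Table 2's column headings allow items to be asked as well as tallied. The attachments are not available, so an unlisted item cannot be excluded. But section 5.2 says it describes the survey contents in full, and its list has no use item, no window and no role for such an item in the outcome.

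The affected group is probably small. Section 9.1 gives priority to clients who will stay for the whole study, section 9.3 allows others to be wait-listed, and usual outpatient stays exceed the study period for clients enrolled early. This stands: the 10-30% range may well be high. The study is also a pilot that calls itself underpowered.

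Finally, under the consent wording in section 10.2, telling research staff about use has the same consequences as telling NUWAY staff, so self-report will be incomplete. This is true, but it already applies to the follow-up question.

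**Conclusion.** The point holds for a defined subgroup: clients discharged on good terms before the exit interview. Their use from discharge to about week 5 has no stated source, their reports for weeks 5 to 9 fall outside the section 5.2 rule, and sections 5.2, 5.3 and 14.1 do not agree on what participants are asked or over what window. Clients discharged between exit and follow-up share the second problem.

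It is tempting to conclude that unobserved time is automatically scored as abstinent. The documents do not say so. They contain no rule for it, and the defect is that nothing prevents that reading.

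The missed recurrence before exit is about 0.7 to 3.6 percentage points, roughly one to four people in 100, on assumed discharge and risk rates that the documents neither give nor bound. A biased comparison further requires the arms to differ in early discharge or in risk, which cannot be shown in advance. The effect is modest, but it falls on a primary outcome and is cheap to prevent, so the change should be made.

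**What to change.** 1. At the exit interview, in both arms, ask the substance-use question already asked at follow-up, covering baseline to exit.
2. Reconcile sections 5.2, 5.3 and 14.1, so that the follow-up and combined scripts cover all time since the last completed interview, or since baseline if there was none.
3. In section 5.2, define recurrence as use shown by the NUWAY record or reported at either research interview between randomisation and follow-up. Align section 5.4 with the record content given in sections 5.2 and 20.2.
4. Code intervals with neither source as missing, not abstinent, and report their number and length by arm.
5. Report the record-only rate as a sensitivity result.

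The cost is one to two minutes in an interview already held and a short addition to section 5.2. The drawbacks are under-reporting over a recall of about five weeks and the section 10.2 disclosure consequences, which would now attach to a second interview.
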